Overview of study approach. In a 24 week RCT based in a large urban area with high rates of OUD and HIV, we will recruit 250 out-of-treatment opioid users from SEPs and randomize 1:1 to onsite BMT initiation (**O-BMT**) or enhanced referral. Over two weeks, participants in the O-BMT arm will see a buprenorphine provider twice, receive prescriptions of medication, and then their care will be transferred to a community health center (CHC) for maintenance BMT. In the control arm, participants will receive enhanced referral to a CHC for initiation and maintenance BMT. We will assess participants with urine drug tests, questionnaires, and medical record review studying treatment engagement, treatment outcomes (opioid use, HIV risk behaviors) and programmatic service utilization in order to establish effectiveness and costs. We will also assess buprenorphine diversion using electronic monitors, urine drug testing, and sequential surveys.

Setting. A. New York Harm Reduction Educators (NYRHE) is the largest harm reduction agency in New York City with over 35 staff members and serving over 5000 clients annually. At two community-based offices and 11 street-side locations, NYHRE provides participants with syringe exchange; referral for medical, dental and addiction treatment; and other supportive services. The majority of NYHRE's clients are Hispanic or black, male, 40-49 years old, and PWID. Diverse staff members (case managers, outreach workers, and syringe exchange staff) have received training on BMT. O-BMT will be offered at community-based offices only.

B. Washington Heights CORNER Project (WHCP) is another harm reduction agency situated in an area highly affected by OUD and HIV. At its community-based office, WHCP provides clients with syringe exchange; referrals for medical, dental, or addiction treatment; and other supportive services. WHCP serves over 1500 clients annually with similar characteristics as NYHRE. WHCP staff members have received training on BMT.

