Aim 1: To test the effectiveness of O-BMT. *H1: more participants randomized to O-BMT (vs. control) will be engaged in BMT at 30 days.* Our primary analysis will determine the effect of the intervention (O-BMT). We will use a chi square test comparing the proportion of participants in each study arm who have an active buprenorphine prescription 30 days after enrollment. We will also conduct a multivariable logistic regression adjusting for mental illness, polysubstance use, and addiction severity.

H2: Reductions in opioid use will be greater among participants randomized to O-BMT (vs. control) over 24 weeks. We will use generalized estimating equations to compare changes in opioid use between study arms over the 24 week study period. One model will use results from urine drug tests at 1, 2, 4, 6, 8, 12, and 24 weeks. A second model will compare the mean number of days (of the prior 30 days) with self-reported opioid use at 4, 8, 12, and 24 weeks.

H3: Reductions in HIV risk behaviors will be greater among participants randomized to O-BMT (vs. referral) over 24 weeks of follow-up. We will use generalized estimating equations to compare changes in injecting risk at 2, 12, and 24 weeks.

Aim 2: To test the safety of onsite buprenorphine treatment at syringe exchange programs.

H4: Diversion of buprenorphine will not be significantly greater among participants randomized to O-BMT (vs. control). By definition, participants who are not prescribed buprenorphine will not have an opportunity to divert their medication, but we will use an intention to treat approach to maintain randomization. The risk difference

Principal Investigator: [name]

threshold margin for non-inferiority will be 5%. We will construct Wald 95% confidence intervals (CIs) for a difference in diversion rates between the two arms and examine if the lower bound of the 95% CI is greater than the threshold margin. If potential confounding factors are unbalanced and require adjustment, we will apply logistic regression and estimate the Odds Ratio (OR) and its CI, examining if the lower bound of the OR is greater than the OR converted from the risk difference.

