D.10 Power analysis. To estimate the effect size for the O-BMT intervention, we drew from prior pilots of onsite treatment. Stancliff et al.⁴² offered BMT to SEP participants (N = 100) and 68% were engaged in BMT at 3 months (30 day engagement was not reported). Tringale et al.⁴³ offered BMT to SEP participants (N=9) over 15 days and then transferred care to treatment program. Following onsite initiation, 33% ultimately engaged in BMT. Daniels et al.⁸⁰ offered BMT at a community-based recovery center (N = 78) and 49% were transitioned to primary care site to continue treatment. For enhanced referral, we estimated rates of engagement in BMT

Principal Investigator: [name]

Table 3. Sample size calculation for hypothesized BMT engagement rates			
Enhanced referral arm	O-BMT arm		
	33%	49%	68%
	0%	40	26
	9%	80	36
	16%	200	62

Note: Sample sizes determined based on Fisher exact test when engagement rate in referral arm is 0.1%. For other tests, the sample sizes were determined based on Chi-square tests.

14%. Though this is larger than tolerable margins for non-inferiority, we will have good estimates of the frequency of diversion in the O-BMT arm, which will provide important safety data for onsite treatment.

For Aim 3, assumptions are based on differences in cost and effect, standard deviations of cost and effect, the correlation of the difference in cost and effect, desired confidence and power levels, and the maximum willingness-to-pay value.^{106,107} We estimated the power for the primary outcomes of our economic analysis (cost-per QALY and cost-per abstinent year) using the target sample size of 250 (125 per group), and a range of values for the aforementioned assumptions, based on prior economic evaluations of substance use disorder interventions. We estimate at least 90% power to be 95% confident that an intervention is acceptable at the commonly cited willingness-to-pay threshold of \$100,000 per QALY.⁹⁵

PROTECTION OF HUMAN SUBJECTS

Human subjects involvement and characteristics: We will enroll 250 participants from syringe exchange programs (SEPs) with opioid use disorder (OUD) who are interested in buprenorphine maintenance treatment (BMT) and are motivated for treatment.

Eligibility criteria include:

- 1) age \geq 18 years
- 2) opioid use disorder by DSM-V criteria
- 3) interest in BMT
- 4) motivation for OUD treatment, based on SOCRATES
- 5) willingness to accept CHC referral

Exclusion criteria include:

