- 1) receiving opioid agonist treatment in the past 30 days (confirmed by NY Prescription Drug Monitoring Program);
- 2) inability to provide informed consent
- 3) unstable mental illness (e.g., suicidality, psychosis, etc.)
- 4) severe alcohol use disorder or benzodiazepine use disorder by DSM-V criteria
- 5) hypersensitivity to buprenorphine or naloxone.
- 6) pregnancy (confirmed via urine testing)

Rationale for inclusion/exclusion criteria: Study participants will include out-of-treatment SEP participants with OUD. We will only include participants who are interested in BMT, motivated for OUD treatment, and willing to accept referral to a CHC for treatment, because our goal is to increase engagement in comprehensive BMT. Providing BMT onsite at SEPs could attract participants who are unready to stop illicit opioid use and only want buprenorphine temporarily to reduce withdrawal symptoms or because they do not have access to their illicit opioid of choice. There may be benefits to this type of symptom treatment, but our study is not designed to evaluate these benefits. We will exclude those with clinical contraindications to BMT,

from our own pilot data and several studies that referred SEP participants to MMT. Engagement after passive referral may be as low as 0%,¹⁴ while referral to MMT has resulted in 9-16% of SEP participants engaging in treatment.³⁷⁻³⁹ Therefore, we will recruit a sample of 250, which allowing for up to 20% attrition (n=200), giving us at least 80% power for the primary outcome (**BMT engagement**) in all proposed scenario.

For Aim 2, we chose the intention to treat analysis as the primary outcome. With a sample size of 250 and an expect rate of diversion of 10-25%, we will only have 80% power to declare that diversion rate in the O-BMT arm is non-inferior to the referral arm if the inferiority margin of the risk difference is 10-

Principal Investigator: [name]

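### Aim 2's switch from a 5-point risk difference to an adjusted odds ratio rests on an undefined imbalance check and an unstated control rate, so the effective non-inferiority margin is not fixed in advance

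*Combined protocol and SAP*

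**What the plan says.** The combined protocol and SAP, under Analysis, Aim 2 (H4), works by intention to treat on the risk-difference scale. The "threshold margin for non-inferiority will be 5" percentage points, and "We will construct Wald 95% confidence intervals (CIs) for a difference in diversion rates between the two arms" describes the interval to be compared with it.

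A conditional second rule follows: "If potential confounding factors are unbalanced and require adjustment, we will apply logistic regression and estimate the Odds Ratio (OR) and its CI". On that scale the non-inferiority decision is made by "examining if the lower bound of the OR is greater than the OR converted from the risk difference".

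The plan does not say:
- which factors are to be checked (Aim 1 names mental illness, polysubstance use and addiction severity for its adjusted model; Aim 2 names none);
- what counts as unbalanced, or when this is judged;
- which control diversion rate converts 5 points into an OR;
- which result decides if the two scales disagree.

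The power section (D.10) gives the expected rates: "With a sample size of 250 and an expect rate of diversion of 10-25%, we will only have 80% power". It attaches that power to a risk-difference margin of 10 to 14 points and concedes that this is wider than would be tolerable. Under Randomization, allocation is stratified by site.

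**The concern.** Diversion is the primary safety outcome, so its decision rule should be reproducible from the text. Here an unquantified judgement about imbalance changes the effect measure, the model and the numerical margin together. Five points on the risk scale do not correspond to one OR. The odds ratio depends on the control rate, and that rate is not given. Two analysts following the same text could apply different margins to the same data and reach opposite conclusions on whether onsite initiation is non-inferior for diversion.

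**Working it through.** **Inputs.** Margin 5 points and Wald 95% interval (Analysis, H4). Expected diversion 10-25% and N = 250 (D.10). Allocation 1:1 (Overview of study approach), hence 125 per arm. Diversion is an adverse outcome, so non-inferiority is taken here as an upper bound below the margin for O-BMT relative to referral. The plan's wording about the lower bound is a separate matter and is set aside.

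**The plan's own figure.** The margin with 80% power at equal rates p is (z₁₋α + z₀.₈₀) × √(2p(1−p)/125). With one-sided α = 0.05 this gives 9.4 points at p = 10% and 13.6 at p = 25%. Rounded up, these are the stated 10 and 14, so 125 per arm and 10-25% are workable inputs. One-sided 0.025, which matches a 95% interval, gives 10.6 and 15.3.

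**Step 1: the converted margin.** OR margin = [(p + 0.05)/(0.95 − p)] ÷ [p/(1 − p)], where p is the control rate.

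| Control rate | OR equal to 5 points |
|---|---|
| 10% | 1.59 |
| 15% | 1.42 |
| 20% | 1.33 |
| 25% | 1.29 |

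**Step 2: reading a fixed OR back as a risk difference.**
- OR 1.59 (set at 10%), true control rate 25%: odds = 1.588 × 0.25/0.75 = 0.529; risk = 0.529/1.529 = 34.6%; permitted excess 9.6 points.
- OR 1.29 (set at 25%), true control rate 10%: odds = 1.286 × 0.10/0.90 = 0.143; risk = 0.143/1.143 = 12.5%; permitted excess 2.5 points.

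**Step 3: false non-inferiority.** Simulation with 400,000 replicates, 125 per arm, a true excess of exactly 5 points and an unadjusted OR.

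| True control rate | Risk difference | OR, observed rate | OR fixed at 10% | OR fixed at 25% |
|---|---|---|---|---|
| 10% | 2.7% | 1.3% | 2.4% | 0.6% |
| 17.5% | 2.7% | 1.8% | 6.6% | 1.5% |
| 25% | 2.5% | 1.9% | 10.9% | 2.5% |

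**Step 4: how often the scale alone decides.** With equal true rates and conversion at the observed control rate, the two tests disagree in about 11% of trials at 10% and 3% at 25%. If the rate were as low as 4%, they would disagree in 37% (risk difference passes in 56%, OR in 19%). In every disagreement the risk difference passes and the OR fails.

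**Step 5: examples (O-BMT vs referral, 125 per arm).**
- 24 vs 31 events: risk-difference upper bound 4.6 points, passes. OR upper bound 1.32: fails against 1.29 (observed rate, 31/125) but passes against 1.59.
- 20 vs 25 events: difference −4.0 points, SE 4.85, upper bound −4.0 + 1.96 × 4.85 = 5.5 points, fails. OR 0.76, upper bound 1.46: passes against 1.59, fails against 1.33 (observed rate) or 1.29.

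**A scenario resting on an assumption.** If 16% of the referral arm were prescribed buprenorphine (the top of the referral engagement range in D.10) and 25% of those diverted, control events would be 125 × 0.16 × 0.25 = 5, or 4%. With 5 vs 5 events the risk-difference upper bound is 4.9 points (passes), while the OR upper bound is 3.54 against a converted 2.37 (fails).

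**The case against.** The strongest reply is that the plan keeps its margin. The OR is explicitly derived from the 5 points, imbalance can be judged on baseline data alone, and the stated 10-25% range could supply the reference rate. That is fair. It disposes of three stronger readings that a reader might infer.

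- *The margin is changed after outcome data are seen.* The documents do not say this. The trigger concerns confounders, and no timing is given.
- *The reference rate has to come from the trial's own data.* The text is silent, and a planning value would be compatible with it.
- *The OR margin becomes several times looser as the control rate falls.* A larger OR at a lower control rate is still 5 points. Converted at the observed rate, the OR test is stricter: at a 4% control rate and a true excess of 5 points, false non-inferiority is 0.6% against 3.3% for the risk difference, and no replicate passed on the OR alone. It is looser only when the reference rate is set below the true one.

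The five-event scenario can also be challenged. D.10 gives 10-25% in its intention-to-treat power sentence, which read as written means 12.5 to about 31 control events. The 0-16% engagement range comes from passive referral and referral to methadone treatment, not from the enhanced referral used here. The composite definition of diversion is also broad.

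Finally, D.10 already concedes weak power. At the 5-point margin it is about 26% (rate 10%) to 15% (rate 25%) at one-sided 0.025. This limits the consequence but does not supply the missing rule.

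**Conclusion.** The point stands as a defect of specification with a measurable effect on the decision. The trigger, the covariates and the numerical OR margin are not fixed in advance, so the adjusted decision rule cannot be reproduced from the text. Within the plan's own 10-25% range the OR margin runs from 1.59 to 1.29. Depending on the unstated reference rate, the adjusted test may be stricter than the risk-difference test or clearly looser, with false non-inferiority of about 11% in place of 2.5% in the worst combination examined. The direction of the effect is therefore undetermined.

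The simulated figures assume 125 per arm with complete data, an unadjusted OR and the upper bound as the criterion. Covariate adjustment shifts the OR only slightly: for a balanced binary covariate with OR 3, the conditional value is 1.61 against 1.59 at 10%, and 1.31 against 1.29 at 25%. The 37% disagreement and the five-event count apply only if control diversion is near 4%, which the documents do not establish. The change should be made, but it does not bear on the trial's primary effectiveness analysis.

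**What to change.** Under Analysis, Aim 2 (H4):

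1. Keep the risk-difference scale in every case. Name one primary analysis in advance: a site-stratified (Mantel-Haenszel) risk difference with its 95% confidence interval, compared with the 5-point margin. Site is the natural stratifier because randomisation already uses it.
2. Delete the imbalance trigger and the conversion of the margin to an OR.
3. If a covariate-adjusted OR is still wanted, name its covariates in advance and label it a sensitivity analysis that does not decide non-inferiority.

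Fixing the OR margin at a stated reference rate would make the rule reproducible, but it would equal 5 points only if the control rate turned out to be that rate. The single risk-difference analysis avoids this.

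The cost is a change of wording. No additional participants, visits or data are needed.

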Aim 2: Primary outcome (safety): We will use a dichotomous measure (yes/no) of **buprenorphine diversion** for all participants to determine how many sell or give away prescribed medication. We will define diversion as having at least one problem behavior over the 24 weeks: non-adherence to prescribed medication on electronic monitoring, self-reported diversion, or a urine sample consistent with diversion. Adherence will be determined weekly with Wisepill adherence for one week equaling $X/7Y$, where X = number of openings in one week and Y = number of doses prescribed per day. For the composite measure, non-adherence will be considered < 90% adherence. We will adapt the MGH Medication Questionnaire, which assesses misuse of prescribed medications, including selling medication, letting others take prescribed medication, or taking medication to get “high”. For the composite measure, self-reported diversion will be defined as an affirmative response to the question, “In the past 2 weeks, have you sold your buprenorphine to others?” We will also test each urine sample for buprenorphine, and if absent among participants prescribed BMT, the urine sample will be considered consistent with diversion. Each behavior will also be explored individually.

Aim 2: Secondary outcomes (safety): We will also report illicit buprenorphine use (i.e., buprenorphine detected in urine samples of participants who are not prescribed BMT), and determine changes in illicit buprenorphine use from baseline to study completion among participants in each study arm.

Aim 3: Primary outcome (incremental cost-effectiveness ratio, ICER): The ICER will be calculated by dividing the incremental mean cost of the O-BMT arm relative to the control arm by the incremental mean effectiveness of the O-BMT arm relative to the control arm (instruments used to measure costs and effectiveness are described in detail below). The primary economic effectiveness outcome will be the quality-adjusted life-year (QALY), a measure that incorporates both duration and health-related quality-of-life and is recommended as the primary economic effectiveness measure.⁹⁴ The QALY captures a wider range of consequences than other clinical effectiveness measures, and permits comparisons across disorders and interventions, allowing for broader economic interpretation. Also, generally accepted value thresholds have been established for QALYs, but not for clinical measures.⁹⁵

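### The attrition allowance is applied only to the record-based Aim 1 outcome; the Aim 2 and Aim 3 power statements assume all 250 are analysed, although Aim 3 wholly and Aim 2 partly depend on research visits to week 24

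*Combined protocol and SAP*

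**What the plan says.** D.10 (Power analysis) treats the three aims differently.

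- **Aim 1.** The outcome here is BMT engagement, and loss is allowed for: "we will recruit a sample of 250, which allowing for up to 20% attrition (n=200), giving us at least 80% power". Main outcome variables defines engagement as an active prescription 30 days after randomization. Under Medical Records, the data come from the health center record and the state prescription monitoring program, which covers controlled substances dispensed by every pharmacy in the state.
- **Aim 2.** Power is stated for a sample of 250 with diversion rates of 10-25%. It is 80% only if the margin is 10-14%, which the plan itself calls wider than tolerable. The Aim 2 analysis section sets a 5% margin and a Wald 95% confidence interval. No attrition is mentioned.
- **Aim 3.** Two measures are named together as "the primary outcomes of our economic analysis (cost-per QALY and cost-per abstinent year". Their power is worked out on everyone randomized, with no mention of attrition: "using the target sample size of 250 (125 per group), and a range of values for the aforementioned assumptions". The conclusion drawn is this: "We estimate at least 90% power to be 95% confident that an intervention is acceptable at the commonly cited willingness-to-pay threshold". The threshold meant is $100,000 for each QALY. The kinds of input are named ("assumptions are based on differences in cost and effect, standard deviations of cost and effect", among others), but no values are given.

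The Aim 3 outcome sections take QALYs from the EQ-5D, and non-study resource use and criminal activity from self-report forms. They list cost per abstinent-year as a secondary outcome and say that "generally accepted value thresholds have been established for QALYs, but not for clinical measures".

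**The concern.** The allowance sits on the outcome that needs it least. A participant who stops attending research visits can still be classified for engagement from records. The same participant contributes no later EQ-5D, resource-use or crime data, so Aim 3 is the aim most exposed to loss, and it has no allowance. Aim 2 is exposed through its survey and urine components.

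The Aim 3 sentence is the plan's only stated support for the cost-effectiveness hypothesis (H5) being answerable at this sample size. If 90% was the lowest value across the sponsor's scenarios, the plan's own attrition figure takes it below 90%. For Aim 2, a power that is already conceded to be limited is stated more favourably than the plan's loss assumption and its planned interval allow.

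**Working it through.** **Inputs from the protocol.** 250 randomized 1:1 (125 per arm); attrition up to 20%, so 200 (100 per arm); earlier retention of 84% over six months (Participant tracking); Aim 2 rates 10-25%, margin 10-14%, 80% power, Wald 95% CI; Aim 3 at least 90% power at 95% confidence.

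**Assumptions.** Normal approximation, equal loss in both arms, complete-case loss, and equal true diversion rates in the two arms. The 10% margin is paired with the 10% rate and the 14% margin with the 25% rate.

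**1. Aim 1, the plan's own figure.** A chi-square test of 16% against 33% at two-sided 0.05 with 80% power needs 200 in total, as in Table 3. Power is 80.3% with 200 and 88.3% with 250. The allowance was therefore built into Aim 1.

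**2. Aim 2, margin that gives 80% power.** Margin = (z_alpha + 0.8416) × sqrt(2p(1−p)/n), with n per arm.

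- n = 125, one-sided 0.05: p = 10% gives 2.4865 × 0.0379 = 9.4%; p = 25% gives 2.4865 × 0.0548 = 13.6%. Rounded up to whole percents, this is the stated 10-14%.
- n = 125, one-sided 0.025 (the planned 95% CI): 10.6% to 15.3%.
- n = 100, one-sided 0.05: 10.6% to 15.2%.

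Of these combinations, only the full 250 with one-sided 0.05 gives the stated range. Attrition was left out, and the confidence level is not that of the planned interval.

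**3. Aim 2, power at the stated margins.** Power = Phi(margin / sqrt(2p(1−p)/n) − z_alpha).

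| Analysed | One-sided level | 10% rate, 10% margin | 25% rate, 14% margin |
|---|---|---|---|
| 250 | 0.05 | 83.9% | 81.9% |
| 200 | 0.05 | 76.2% | 73.9% |
| 250 | 0.025 | 75.0% | 72.4% |
| 200 | 0.025 | 65.4% | 62.8% |

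Example, 200 analysed at one-sided 0.05: 0.10/0.0424 − 1.645 = 0.712, and Phi(0.712) = 76.2%. The first row exceeds 80% because the margins were rounded up.

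**4. Aim 3.** The 90% cannot be reproduced, because no cost difference, effect difference, standard deviation or correlation is given. Only scaling is possible: power at fraction r followed = Phi((z_alpha + z_power) × sqrt(r) − z_alpha).

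- Exactly 90% at 250, r = 0.80, two-sided 0.05: (1.960 + 1.2816) × 0.8944 − 1.960 = 0.939, so 82.6%. With one-sided 0.05 it is 83.5%.
- r = 0.84: 84.4% (two-sided) or 85.0% (one-sided).
- If power at 250 were 95%, it would be 89.7-90.3% at 200. About 95% is therefore needed at 250 to keep 90% at 200.

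**5. Missing-data provisions.** The Analysis section keeps lost participants under intention to treat. The Missing data paragraph describes multiple imputation for categorical data only. Costs and EQ-5D weights are modelled by generalized linear models, and no method is stated for missing values of these.

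**The case against.** The strongest reply concerns Aim 3. The plan says at least 90% over a range of undisclosed inputs. A reader might infer that Aim 3 power is really about 83%. The documents do not show that: 83% follows only if the least favourable scenario gave exactly 90%, and with somewhat more power at 250 the claim could survive the loss. The scaling also takes the full 20% as complete-case loss, whereas the plan says up to 20%, cites 84% retention, and fits models at each time point, so that dropouts' earlier data can count. This stands. It makes the Aim 3 figure a conditional floor, but does not supply the missing allowance.

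For Aim 2, a reader might scale a nominal 80% to about 71% and call the aim visit-based. Neither is supported. At the stated margins, the powers with 200 analysed are those in the table. The composite also includes electronic monitoring, which reports in real time during the first two weeks of treatment, and participants never prescribed buprenorphine are non-diverters by definition, known from records. Visit loss of 20% need not remove 20% of the Aim 2 sample; part of its effect would be missed diversion. It is also fair that the plan concedes weak power here. At the 5% analysis margin with the 95% CI, power is only 15-26% at 250 and 13-22% at 200, so attrition is not the main limit on Aim 2.

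A reader might also infer that no power can be computed for cost per abstinent-year. That goes too far: the plan names maximum willingness to pay among its assumptions, and a value could be assumed. The supportable point is that none is stated for this outcome and the reported power is per QALY.

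Finally, Aim 1 does not have to be re-powered at 88%. Allowing for loss on a record-based outcome is conservative. The 88% holds only if 16% and 33% are rates among all randomized. If they apply to the 80% followed and the rest count as not engaged (an assumption), the rates become 12.8% and 26.4%, and power at 125 per arm is about 78%.

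**Conclusion.** The point holds in this limited form. The attrition allowance is attached only to Aim 1, and the Aim 2 and Aim 3 power statements omit it.

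- **Aim 2:** with 200 analysed, power at the stated margins is about 74-76% at one-sided 0.05, against 82-84% with 250. With the planned 95% interval it is 72-75% at 250 and 63-65% at 200. The figures at 200 are complete-case worst cases. The fall to 72-75% comes from the confidence level alone and does not depend on attrition.
- **Aim 3:** the stated power cannot be verified. It could be as low as about 83% with 200 analysable (84-85% at 84% retention) if 90% was the minimum. Whether it actually falls below 90% depends on inputs that only the sponsor has.
- **Cost per abstinent-year:** it is secondary in the outcome section and primary in D.10, and no willingness-to-pay value is stated for it.

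This should be corrected, but it does not threaten the primary outcome.

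**What to change.** 1. Recompute Aim 3 power from the sponsor's own inputs with 200 analysable, and state the inputs and the result. It may be as low as about 83% if 90% was the minimum at 250.
2. Restate Aim 2 for 200 analysable at the confidence level of the planned interval: either the power at the 10-14% margins (63-65% in the worst case) or the margin that gives 80% power. Say which components do not need visits.
3. Limit the Aim 3 power claim to cost per QALY at $100,000, and label cost per abstinent-year as secondary in D.10, to agree with the outcome section.
4. Leave the Aim 1 statement as it is.

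The cost is one recomputation and changes of wording, with no added participants. The downside is that two stated powers become less favourable.

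### The Aim 2 power statement (80% at a 10-14 point margin, no alpha given) does not fit the planned Wald 95% interval, and power at the 5-point margin, 26% to 15%, is never stated

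*Combined protocol and SAP*

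**What the plan says.** The Aim 2 paragraph of D.10 Power analysis reads "With a sample size of 250 and an expect rate of diversion of 10-25%, we will only have 80% power" to declare O-BMT non-inferior to referral "if the inferiority margin of the risk difference is 10" to 14 points. It states neither alpha nor sidedness, and it names one range of diversion rates with no difference between arms. It then qualifies itself: "14%. Though this is larger than tolerable margins for non-inferiority, we will have good estimates of the frequency of diversion in the O-BMT arm". The Aim 3 paragraph of D.10 gives the "target sample size of 250 (125 per group").

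The analysis is set out under Aim 2, H4, in the Analysis section. The "threshold margin for non-inferiority will be 5" per cent on the risk-difference scale. "We will construct Wald 95% confidence intervals (CIs) for a difference in diversion rates between the two arms", and the decision is to "examine if the lower bound of the 95% CI is greater than the threshold margin". The analysis is by intention to treat, and the plan accepts that "participants who are not prescribed buprenorphine will not have an opportunity to divert their medication".

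**The concern.** D.10 and the H4 analysis describe two different tests. D.10 reports power at 10 to 14 points with no alpha. H4 uses 5 points and a 95% interval. A reader who takes the 80% at face value would expect the planned interval to deliver it at those margins. The same reader finds no power figure for the margin that decides H4.

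Diversion is the primary safety outcome of Aim 2. If the 5-point test will probably fail even when diversion is the same in both arms, a failed H4 could be misread as a sign that onsite treatment increases diversion. The plan should say this before the data are seen.

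The rule itself is also incomplete. H4 does not say which arm is subtracted from which, or whether the margin is +5 or -5 points. Read literally as O-BMT minus referral against +5, a lower bound above the margin would demonstrate excess diversion.

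**Working it through.** **Inputs.** 125 per arm (D.10, Aim 3 paragraph; 1:1 allocation under Randomization). Diversion rate p of 10% or 25% (D.10). Margins m of 10 and 14 points (D.10) and 5 points (H4). Wald 95% interval with one bound compared with the margin, so z = 1.96 (H4). Assumption: equal true rates, since D.10 names no difference. Rule as read here: the upper bound of O-BMT minus referral is below +m.

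**Formulas.**
- SE = sqrt(2p(1-p)/125)
- Power = Phi(m/SE - z)
- Margin for 80% power = (z + 0.8416) × SE

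SE = sqrt(0.18/125) = 0.0379 at 10%, and sqrt(0.375/125) = 0.0548 at 25%.

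**1. The plan's own figure.** With one-sided 5% (z = 1.645), the margins for 80% power are 2.4865 × 0.0379 = 9.4 points and 2.4865 × 0.0548 = 13.6 points. These round up to 10 and 14. Power at 10 and 14 points is 83.9% and 81.9%; with Farrington-Manning variance it is 81.2% and 81.8%. The stated 80% therefore fits a one-sided 5% test. That is an inference, because D.10 gives no alpha.

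**2. The planned interval at the D.10 margins (z = 1.96).**

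| Diversion | Margin | m/SE | Power | Exact enumeration | Margin for 80% power |
|---|---|---|---|---|---|
| 10% | 10 points | 2.635 | Phi(0.675) = 75.0% | 75.4% | 10.6 points |
| 25% | 14 points | 2.556 | Phi(0.596) = 72.4% | 72.5% | 15.3 points |

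Continuity-corrected and Farrington-Manning versions at one-sided 2.5% were also run, and none reached 78% at either end.

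**3. The planned interval at the 5-point margin.**

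| Diversion | m/SE | Power | Exact enumeration | 95% half-width |
|---|---|---|---|---|
| 10% | 1.318 | Phi(-0.642) = 26.0% | 26.4% | 1.96 × 0.0379 = 7.4 points |
| 25% | 0.913 | Phi(-1.047) = 14.8% | 14.9% | 1.96 × 0.0548 = 10.7 points |

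At one-sided 5% the figures would still be only 37% and 23%. For 80% power at 5 points, the planned interval would need 566 per arm (10% diversion) or 1,178 per arm (25%).

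**4. What must be observed to pass at 5 points.**
- With 13/125 (10.4%) diverting in referral, O-BMT may have at most 10/125 (8.0%): upper bound 4.8 points, against 5.7 with 11/125.
- With 31/125 (24.8%) in referral, O-BMT may have at most 24/125 (19.2%): upper bound 4.6 points, against 5.5 with 25/125.
- Equal counts pass at 5 versus 5 (4.0% each, half-width 4.86 points) and fail at 6 versus 6 (5.30 points).

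**5. Sensitivity to equal rates (5-point margin, unpooled SE).**

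| True O-BMT minus referral | Referral 10% | Referral 25% |
|---|---|---|
| 2 points lower | 49% | 25% |
| Equal | 26% | 15% |
| 2 points higher | 11% | 8% |
| Needed for 80% power | 4.5 points lower | 9.2 points lower |

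**The case against.** The 80% is not a slip of arithmetic. It reproduces at one-sided 5%, and moving to the planned level shifts the required margins only from the printed 10-14 to 10.6-15.3 points. At the D.10 margins, a true O-BMT rate about 0.5 points (10% diversion) or 1.2 points (25%) lower would restore 80%. The plan already calls 10-14 points too wide, says it will have only 80% power there, and takes its sample size from Aim 1. All of this stands. The mismatch in alpha is modest, and the plan is candid in words that tolerable margins are underpowered. But the concession carries no number, H4 keeps the 5-point test, and the fallback it offers is an estimate for one arm, whereas H4 compares two.

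The second objection is that equal intention-to-treat rates may be unrealistic. Someone never prescribed buprenorphine cannot divert it, and D.10 assumes far more engagement in O-BMT (33-68%) than after referral (0-16%). The plan does not say whether 10-25% applies to everyone randomised or only to those prescribed. If it applies to those prescribed, and engagement is 9-16% in referral and 33-68% in O-BMT, power at 5 points runs from about 39% down to near zero. In several of those cases the true difference exceeds 5 points, so failing the test would be the right answer. This is fair, and it means that 26% to 15% must be labelled as the equal-rates case. It gives no support to the stated 80%. The plan also argues in Background that onsite treatment could reduce diversion, which would raise power. The dependence on the assumption is a further reason to state it.

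The direction of the decision rule is a separate defect. It belongs here only because no power can be attached to a rule whose direction is not given. The rule would work as referral minus O-BMT against -5 points, but the plan does not say so.

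**Conclusion.** The concern holds. Under equal true rates and 125 per arm, the planned Wald 95% interval delivers 75% and 72% power at the two ends of the range for which D.10 states 80%. At the 5-point margin that decides H4 it delivers 26% to 15%, a figure the plan never gives. When diversion is truly equal, the test would fail about 74% to 85% of the time. In the expected range, H4 can be declared only if observed diversion is lower in O-BMT, by about 2.4 points (3 participants) at the low end and 5.6 points (7 participants) at the high end.

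The shortfall at 10-14 points is the smaller part and most likely reflects an unstated one-sided 5% level. The missing figure at 5 points is the larger part. The results rest on equal rates, all 250 participants being analysed, and the upper-bound reading of the rule. If 20% attrition also applied to Aim 2 (100 per arm), power at 5 points would be 22% to 13%.

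**What to change.** 1. In D.10, replace the Aim 2 power text with wording to this effect: With 125 per arm, equal true diversion rates and a Wald 95% CI (one-sided 2.5%), 80% power requires a margin of 10.6 points (10% diversion) to 15.3 points (25% diversion). At the planned 5-point margin power is 26% to 15%, and lower if intention-to-treat diversion is higher in the O-BMT arm because more of its participants are prescribed buprenorphine. The expected 95% CI half-width is 7.4 to 10.7 points. H4 will be reported as a risk difference with its 95% CI; failing the 5-point criterion is not by itself evidence of greater diversion. It would help to add whether the 10-25% refers to participants randomised or to participants prescribed.

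2. In the H4 analysis, state that non-inferiority is declared if the upper bound of the 95% CI for O-BMT minus referral is below +5 points. The adjusted odds-ratio rule that follows uses the same lower-bound wording and should be given the same direction.

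The cost is text edits in two places, with no new data, analysis or change in sample size. The downside is that the stated power becomes less favourable and the plan says openly that H4 is unlikely to be confirmed at this sample size.
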